#### 7.5 Secondary Endpoints

- i. Comparison of long-term toxicities related to eBx vs. Mohs treatment;
- ii. Comparison of long-term cosmetic outcomes for lesions treated for NMSC with eBx vs. Mohs;
- iii. Chronic toxicities;
- iv. Patient Survey for reporting Patient Reported Outcomes (PRO)

#### 7.6 Eligibility Criteria

#### 7.6.1 Inclusion Criteria

All answers must be YES to have lesions included in this study.

- 1. Previously completed treatment for non-melanoma skin cancer using Xoft eBx Electronic Brachytherapy System or Mohs surgery;
- 2. Provides informed Consent;
- 3. Greater than 40 years of age;
- 4. Pathological diagnosis confirmed to be squamous cell or basal cell carcinoma prior to treatment;
- 5. Cancer Staging included in this study:
  - Stage 0: Tis, N0, M0
  - Stage 1: T1, N0, M0
  - Stage 2: T2, N0, M0 and  $\leq$  4cm in diameter

#### 7.6.2 Exclusion Criteria

All answers must be NO to have lesions included in this study.

- 1. Target area is adjacent to a burn scar
- 2. Any prior definitive surgical resection of the cancer, prior to Radiation Treatment
- 3. Known perineural invasion
- 4. Actinic Keratosis
- 5. Known spread to regional lymph nodes
- 6. Known metastatic disease

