#### 8 METHODOLOGY

#### 8.1 Identifying the Population

The first phase of this study will be to identify patients who completed treatment with eBx or Mohs treatment approximately 3 years ago or more prior to study onset and collect history and demographic data, and eligibility and treatment planning and treatment data retrospectively from the patient records and on source worksheets to complete a matched pair cohort study comparison.

This phase will include a review of the site's patient medical records to determine if the source documentation contains the variables that are needed to determine eligibility and which will be used in the endpoint analyses. These variables include:

- Patient Age (within  $\leq 15$  year brackets)
- Pathology report for evidence of:
  - Lesion size (cm)
  - Lesion diagnosis (BCC, SCC)
- Last treatment date for each location
- Lesion location (e.g. face, extremities, neck, nose, scalp, torso)
- Toxicities at time of prospective follow-up visit

Matching will be performed according to:

- Calendar year of treatment for equivalent follow-up
- Patient age bracket [15-year brackets or less]
- Lesion diagnosis (BCC, SCC)
- Lesion size range (< 1 cm,  $\geq$ 1 and <2 cm,  $\geq$ 2 and <3 cm,  $\geq$ 3 and  $\leq$ 4 cm)
- Location according to the methodology below:
  - o Scalp
  - Face (includes neck)
  - o Nose
  - o Ear
  - o Torso
  - Upper extremities (Arms, hands, fingers)
  - Legs (Thighs, lower leg, feet, toes)

Data Collected Prospectively:

- Cosmesis rating by physician
- Cosmesis rating by the patient
- Recurrence of cancer
- Chronic toxicities
- Patient reported outcomes (PRO) survey

Patients who return for long-term follow-up will be required to provide informed consent for both the retrospective data and the prospective data that are collected at the time of the visit.

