#### 8.2 Long-term Follow-up Visits

Each patient agreeable to participating in this study will be asked to return for an office visit for prospective data collection. There may be up to two (2) visits over the next years.

Since the subjects have already received treatment, the study cannot include a randomization design. Each lesion from the eBx treatment group will be matched to a lesion treated with Mohs surgery. The variables used for matching will be:

- Calendar year of treatment for equivalent follow-up
- Patient age bracket [Attempt to ensure 15-year brackets or less]
- Lesion diagnosis (BCC or SCC)
- Lesion size range (< 1 cm,  $\geq$ 1 and <2 cm,  $\geq$ 2 cm and <3 cm,  $\geq$ 3 and  $\leq$ 4 cm)
- Lesion Location

It is not expected that there will be an equal number of patients treated with eBx and Mohs at each site, as some practices may not use both types of treatment modalities. To ensure that a minimum of 293 lesions are matched, the participating sites will be asked for a list of all patients treated approximately 2 to 4 years prior to study onset including the variables being used for matching. The study sponsor will then compare all the available data from the participating sites and notify each site which patient and lesion data will be included in the study.

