#### **12 STATISTICAL CONSIDERATIONS**

#### 12.1 Data Collection

Data will be collected at the study site on case report forms and will be entered into the online database by ECR personnel. The following data collection requirements are listed below:

Form # and Name	Retrospective Chart Review	Prospective Follow-up and Data Collection
Demographics and History	Х	
Eligibility	Х	
Treatment Planning and Treatment	Х	
Follow-up Including Cosmesis, Chronic Toxicities, Recurrence		Х
Patient Reported Outcomes (PRO) Survey		Х

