#### Table 1. Case Report Forms

#### **12.2 Statistical Analyses**

This is a multi-center, retrospective-prospective study comparing non-melanoma skin cancer treatment (basal cell carcinoma and squamous cell carcinoma) using Xoft electronic brachytherapy (eBx) results compared to a Mohs micrographic surgery. The lesion data will be matched on 4 categories as outlined in Section 8 and the results will be compared between the two treatment groups.

A sample size calculation comparing treatment of NMSC with eBx to treatment with Mohs micrographic surgery was done using a 1.5% historical 3-year recurrence rate for NMSC treated with Mohs, and a 2.5% non-inferiority margin. A total of 293 lesions for each treatment group will provide 80% power with a 0.05 alpha level of significance. Data from up to three hundred-twenty (320) subjects with each type of treatment will be collected to ensure a sufficient number of lesions to adequately power the study. There may be more than one lesion per patient that is matched to another lesion in the other treatment group. The total lesions will be compared in this study and the lesion count determines the number of patients that are ultimately enrolled.

The primary endpoint of freedom from recurrence and the secondary endpoints will be summarized for each treatment group and Chi-square tests performed as applicable. All tests will be 2-sided, with significance level set at 0.05, and performed using SAS (version 9.4 SAS Institute, Inc., Cary, NC).

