#### **15.2 CASE REPORT FORM**

Provided as a separate document in the form of a worksheet to use as a source document. The final case report form will be electronic data capture.

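### Exclusion 2 bars prior definitive resection only before radiation, so a previously resected, recurrent lesion can enter the Mohs group but not the eBx group

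*Combined protocol and SAP*

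**What the plan says.** All references are to the combined protocol and SAP.

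- **Section 7.6.2** gives one exclusion list for every lesion in the study. Item 2 is "Any prior definitive surgical resection of the cancer, prior to Radiation Treatment". No counterpart is written for resection before Mohs.
- **Section 7.6.1** admits a lesion on the basis of "Previously completed treatment for non-melanoma skin cancer using Xoft eBx Electronic Brachytherapy System or Mohs surgery", with limits on age, pathology and stage (Stage 0 to 2, N0, M0, at most 4 cm). It does not require a primary or previously untreated lesion.
- **Section 8.2** states that "Each lesion from the eBx treatment group will be matched to a lesion treated with Mohs surgery". The matching variables in sections 8.1 and 8.2 are calendar year of treatment, age bracket, diagnosis, size range and location. Section 8.2 also expects that "some practices may not use both types of treatment modalities".
- **Sections 8.1 and 12.1** describe the records: sites "collect history and demographic data, and eligibility and treatment planning and treatment data retrospectively", and the forms include one for "Demographics and History" and one for eligibility. Section 15.2 says the case report form is "Provided as a separate document in the form of a worksheet to use as a source document", so its items cannot be seen here.
- **Section 12.2** sizes the study "using a 1.5% historical 3-year recurrence rate for NMSC treated with Mohs, and a 2.5% non-inferiority margin", with 293 lesions per group, 80% power and alpha 0.05. It plans group summaries and 2-sided Chi-square tests, with no adjustment, stratification or sensitivity analysis.

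**The concern.** The study is not randomised, so its comparability rests on eligibility and matching. An eligibility rule that works on one side only undermines that. Followed as written, exclusion 2 keeps previously resected lesions out of the eBx group and lets them into the Mohs group, and nothing later in the plan corrects for this.

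If previously resected lesions recur more often or scar worse, the Mohs results for recurrence, toxicity and cosmesis would look worse than they would for lesions like those in the eBx group. For a non-inferiority claim that is the anti-conservative direction, because a raised comparator rate makes it easier for eBx to appear within the margin.

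There is also a risk of inconsistent use. A Mohs-only practice has no radiation to which the item could refer. One site might disregard it, while another might apply it to any prior resection.

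**Working it through.** **1. The text.** The possible safeguards were checked in turn.

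| Possible safeguard | Does it stop a previously resected lesion entering the Mohs group? |
|---|---|
| Exclusion 2 (7.6.2) | Not if read literally; it is tied to radiation |
| Other exclusions (7.6.2) | No; excluding known perineural, nodal or metastatic disease removes some high-risk recurrences only |
| Inclusion criteria (7.6.1) | No; nothing on prior treatment |
| Matching (8.1, 8.2) | No; five variables, none of them prior treatment |
| Calling of Mohs patients (8.1.1) | No; consecutive, subject to matching |
| Analysis (12.2) | No; unadjusted Chi-square |

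**2. The plan's own figure.** With 1.5% recurrence in both groups, a margin of 0.025 and unpooled variance:

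n = 2 × 0.015 × 0.985 × (1.645 + 0.842)² / 0.025² = 292.3, so 293 per group, with power 80.1%.

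This reproduces the stated 293 at one-sided 0.05. One-sided 0.025 would need 372, and gives 70.2% power at 293. One-sided 0.05 is therefore used below, although section 12.2 names only 2-sided tests.

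**3. Illustrative inputs.** The documents supply neither of these, so both are assumptions:

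- f = share of Mohs lesions previously resected
- RR = their recurrence risk relative to Mohs lesions not previously resected

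The mixed Mohs rate is the not-previously-resected rate times k = 1 − f + f × RR. Three scenarios are shown: f=5%, RR=2 (k=1.05); f=20%, RR=3 (k=1.40); f=30%, RR=4 (k=1.90). In each, eBx is truly 2.5 points worse than Mohs lesions not previously resected.

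The planning rate of 1.5% can be read in two ways:

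- **Reading A:** it is the rate for lesions not previously resected. Then pE = 4.0% and pM = 1.5% × k.
- **Reading B:** it is a mixed-population rate. Then pM = 1.5% and pE = 1.5%/k + 2.5%.

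**4. Chance of declaring non-inferiority.** P = Φ((0.025 − (pE − pM))/SE − 1.645), with SE = √(pE(1−pE)/293 + pM(1−pM)/293). Without the asymmetry P = 5.0% under both readings.

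| Scenario | A: pM / pE | A: P | B: pM / pE | B: P |
|---|---|---|---|---|
| f=5%, RR=2 | 1.575% / 4.0% | 5.6% | 1.5% / 3.929% | 5.6% |
| f=20%, RR=3 | 2.10% / 4.0% | 11.1% | 1.5% / 3.571% | 9.4% |
| f=30%, RR=4 | 2.85% / 4.0% | 22.8% | 1.5% / 3.289% | 14.0% |

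Worked case (f=20%, RR=3, reading A): pE − pM = 0.019 and SE = 0.01419, so P = Φ(0.006/0.01419 − 1.645) = Φ(−1.222) = 11.1%.

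At one-sided 0.025 the chance is 2.5% without the asymmetry, and 2.8%, 5.2-6.2% and 8.1-14.4% with it.

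**5. The test the plan names.** This is the chance that a 2-sided 0.05 Chi-square test detects the same 2.5-point deficit (pooled-variance normal approximation, 293 per group).

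| Scenario | A: without → with asymmetry | B: without → with asymmetry |
|---|---|---|
| f=5%, RR=2 | 46% → 43% | 47% → 44% |
| f=20%, RR=3 | 46% → 27% | 52% → 36% |
| f=30%, RR=4 | 46% → 12% | 57% → 29% |

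**The case against.** The case for leaving the item alone has several parts.

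- **It may have been meant for both groups.** There is one list and one eligibility form, and the item opens broadly, so a site could apply it to every lesion. No passage says that a resected lesion has entered the Mohs group. This stands as a possible reading, but the text does not settle it.
- **The radiation wording has a plausible purpose.** Section 5 separates adjuvant radiation after resection from radiation as primary treatment, and section 4 describes the patients in this study as having primary radiation. The item may simply keep adjuvant radiation out of the eBx group. That explains the wording but leaves the asymmetry.
- **Direction and size are assumed.** This stands. Nothing in the documents shows that previously resected lesions recur more often after Mohs, and f and RR have no source. At f=5%, RR=2, the expected excess is 293 × 0.00075 = 0.22 recurrences. The largest figures need 30% of Mohs lesions previously resected at four times the risk.
- **Other confounding may outweigh it.** Section 4 says radiation was chosen where resection was not an option. That selection may act in either direction, so the net bias of the study is uncertain.
- **Prior resection may already be recorded, and selection is partly central.** The forms are not visible here, and under section 8.2 the sponsor decides which lesions are included. Both points reduce the concern. Neither supplies a rule on prior resection or a use for the data.
- **The amendment comes late.** First follow-up visits were planned from August 2016, and this revision is dated March 2017. A new eligibility rule cannot undo earlier inclusions, which is why the fix also needs an analysis step.

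**Conclusion.** The concern holds. On a literal reading the two groups have different eligibility rules for prior resection, and neither matching nor analysis deals with it. On the looser reading the item is ambiguous, which is also a fault where comparability depends on eligibility.

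The size is unknown. Under the stated assumptions (eBx truly 2.5 points worse, one-sided 0.05, 293 per group) the chance of wrongly declaring non-inferiority ranges from barely changed to several times its nominal level. The direction in favour of eBx depends on RR being above 1 and refers to this asymmetry alone. Confidence is medium: the gap in the text is clear, but its practical effect cannot be established from the documents. The correction is inexpensive enough that it should be made.

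**What to change.** 1. **Reword exclusion 2** so that one rule covers both groups, for example: *any prior definitive surgical resection of the target lesion before the index eBx or Mohs treatment*.
2. **Check the history and eligibility forms.** Confirm that prior resection of the site is recorded in both groups, add the item if it is not, and report its frequency by group.
3. **For lesions already enrolled,** keep the planned primary analysis and add a sensitivity analysis of the primary endpoint restricted to pairs in which neither lesion was previously resected.

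**Cost.** This takes a one-line amendment, a form check with at most one added item, and replacement of some Mohs candidates from the site lists. Each replacement must still match and consent.

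The restricted analysis loses pairs, 293 × (1 − f) being kept. Its power, at equal true rates and one-sided 0.05, would be:

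| f (with RR as above) | Pairs kept | Power, reading A | Power, reading B |
|---|---|---|---|
| 5% | 278 | 78% | 80% |
| 20% | 234 | 72% | 84% |
| 30% | 205 | 67% | 89% |

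The number of pairs kept is not known in advance, so this analysis should be supportive only.

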#### 8 METHODOLOGY

#### 8.1 Identifying the Population

The first phase of this study will be to identify patients who completed treatment with eBx or Mohs treatment approximately 3 years ago or more prior to study onset and collect history and demographic data, and eligibility and treatment planning and treatment data retrospectively from the patient records and on source worksheets to complete a matched pair cohort study comparison.

This phase will include a review of the site's patient medical records to determine if the source documentation contains the variables that are needed to determine eligibility and which will be used in the endpoint analyses. These variables include:

- Patient Age (within  $\leq 15$  year brackets)
- Pathology report for evidence of:
  - Lesion size (cm)
  - Lesion diagnosis (BCC, SCC)
- Last treatment date for each location
- Lesion location (e.g. face, extremities, neck, nose, scalp, torso)
- Toxicities at time of prospective follow-up visit

Matching will be performed according to:

- Calendar year of treatment for equivalent follow-up
- Patient age bracket [15-year brackets or less]
- Lesion diagnosis (BCC, SCC)
- Lesion size range (< 1 cm,  $\geq$ 1 and <2 cm,  $\geq$ 2 and <3 cm,  $\geq$ 3 and  $\leq$ 4 cm)
- Location according to the methodology below:
  - o Scalp
  - Face (includes neck)
  - o Nose
  - o Ear
  - o Torso
  - Upper extremities (Arms, hands, fingers)
  - Legs (Thighs, lower leg, feet, toes)

Data Collected Prospectively:

- Cosmesis rating by physician
- Cosmesis rating by the patient
- Recurrence of cancer
- Chronic toxicities
- Patient reported outcomes (PRO) survey

Patients who return for long-term follow-up will be required to provide informed consent for both the retrospective data and the prospective data that are collected at the time of the visit.

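### A lesion treated with both eBx and Mohs is not tied to its first treatment, so a failure of that treatment can go uncounted

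*Combined protocol and SAP*

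**What the plan says.** - **Entry (7.6.1).** Inclusion 1 reads "Previously completed treatment for non-melanoma skin cancer using Xoft eBx Electronic Brachytherapy System or Mohs surgery". Either modality satisfies it. No section says what happens to a lesion that had both.
- **Earlier treatment (7.6.2).** The only relevant exclusion is "Any prior definitive surgical resection of the cancer, prior to Radiation Treatment". Nothing bars radiation before Mohs, or a recurrent lesion. The list applies to the whole study, not to one group.
- **Date (8.1).** The chart variables include "Last treatment date for each location" and no other treatment date. Matching uses the calendar year of treatment (8.1, 8.2) without saying which treatment.
- **Matching (8.2).** "Each lesion from the eBx treatment group will be matched to a lesion treated with Mohs surgery". Whether the lesion was primary or recurrent is not a matching variable. Sites list patients treated roughly 2 to 4 years before onset, and the sponsor decides which lesions enter.
- **Order (8.1.1).** eBx patients are settled first, and Mohs patients are then called to match them.
- **Outcome (7.4, 12.1).** The primary endpoint is judged at the prospective visit, and the form that holds recurrence is ticked only in the prospective column. Sections 2 and 7.1 do say that existing chart data will be collected.

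**The concern.** Re-treatment after local failure is direct evidence of the primary outcome. If the later treatment can decide a lesion's group, its start of follow-up or whether it is in the study at all, then these depend on the outcome being compared.

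For a lesion that failed eBx and was then treated with Mohs, two things are at stake. The eBx failure may not appear in the eBx rate. The lesion may also enter the Mohs group with already irradiated skin, so that Mohs toxicity and cosmesis ratings partly reflect the earlier radiation. For a lesion that failed Mohs and was then irradiated, the risk is that it leaves the study and the Mohs failure goes with it. With so few recurrences expected, a handful of such lesions matters.

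**Working it through.** **Step 1. Follow two hypothetical lesions through the rules.** Take August 2016, when the first follow-up visits start (section 2), as study onset. Two to four years earlier is August 2012 to August 2014.

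| Rule | eBx 2013, failed, Mohs early 2014 | Mohs 2013, failed, eBx early 2014 |
|---|---|---|
| Inclusion 1 | met through either treatment | met through either treatment |
| Exclusion 2 | not triggered | triggered, if Mohs counts as definitive resection |
| Date in 8.1, read literally | 2014 (Mohs) | 2014 (eBx) |
| Window | both treatments inside | both treatments inside |
| Result | can enter as eBx (2013) or as Mohs (2014) | barred from eBx; read study-wide, barred altogether |

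The first lesion must still meet the stage, size, perineural, nodal and metastatic criteria and match an eBx lesion. If its eBx fell before the window, it was never an eBx candidate, but it could still enter as an irradiated Mohs lesion.

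Keeping the first lesion in eBx does not by itself recover the failure. If Mohs cleared the tumour, the site is free of recurrence at the visit, and 7.4 can score it as a success.

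**Step 2. Reproduce the plan's sample size.** Section 12.2 gives "1.5% historical 3-year recurrence rate for NMSC treated with Mohs", "a 2.5% non-inferiority margin" and "A total of 293 lesions for each treatment group will provide 80% power with a 0.05 alpha level of significance". With equal true rates and unpooled variance:

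n = (z₀.₉₅ + z₀.₈₀)² × 2p(1 − p) / δ² = (1.645 + 0.842)² × 2 × 0.015 × 0.985 / 0.025² = 292.3, so 293.

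The match needs a one-sided alpha of 0.05. One-sided 0.025 gives 372. Section 12.2 also states "All tests will be 2-sided, with significance level set at 0.05", so both levels are shown below.

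**Step 3. Size of one lesion.**
- One uncounted failure: 1/293 = 0.34 points.
- Expected recurrences per group at 1.5%: 293 × 0.015 = 4.4, so one lesion is 1/4.4 = 23% of them.
- The whole margin: 293 × 0.025 = 7.3 lesions.
- If a moved lesion has an assumed 1.5% to 10% chance of recurring again after Mohs, the expected shift in the difference is 0.341 × 1.015 to 0.341 × 1.10, or 0.35 to 0.38 points.

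**Step 4. Sensitivity to the number moved.** The documents give neither the share of eBx failures reclassified nor the recurrence rate after salvage Mohs. The ranges assumed are 0% to 50% and 1.5% to 10%. Set the true rates at the margin: eBx 4.0% (293 × 0.04 = 11.7 failures) and Mohs 1.5%. Let k failures leave eBx and enter Mohs:

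- eBx rate = (11.72 − k)/(293 − k)
- Mohs rate = [(293 − k) × 0.015 + k × r]/293, where r is the recurrence rate after salvage Mohs

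The chance of declaring non-inferiority sums exact binomial probabilities for a Wald upper limit below 2.5 points, with 293 independent lesions per group.

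| Share moved | k | eBx rate | Mohs rate | Chance, one-sided 0.05 | Chance, one-sided 0.025 |
|---|---|---|---|---|---|
| 0% | 0 | 4.00% | 1.50% | 6.9% | 3.5% |
| 10% | 1.17 | 3.61% | 1.50–1.53% | 11.6–12.0% | 6.4–6.6% |
| 25% | 2.93 | 3.03% | 1.50–1.58% | 23.7–25.4% | 14.5–15.8% |
| 50% | 5.86 | 2.04% | 1.50–1.67% | 59.8–63.6% | 45.1–49.3% |

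Nearly all of the change comes from failures missing from eBx. The Mohs rate hardly moves. The table assumes that each moved failure would otherwise have counted as an eBx event, and that no Mohs failures are lost in the other direction.

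**The case against.** Four arguments on the other side carry weight.

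1. **The date probably means the last session of one course.** That fits the protocol's repeated reference to completed treatment. It weakens the literal reading of 8.1, but it does not supply a rule for a lesion with two courses.
2. **eBx patients are settled first (8.1.1).** A lesion whose eBx lies in the window may be reached there and stay in eBx. This lowers the risk, but calling order is not an attribution rule. It also does not help if the endpoint is then scored only at the visit.
3. **Later Mohs may be rare after eBx.** Section 4 describes radiation as chosen where resection was not an option. That makes the switch less likely, not impossible.
4. **Other material could settle it.** The case report form is a separate document (15.2) and the schema in 8.3 was not available. Either might define the index treatment.

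A reader might also infer three stronger things that the documents do not support:

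- *That the protocol moves eBx failures into the Mohs group.* It is silent. Such a lesion also qualifies as an eBx lesion.
- *That the eBx failure is charged to Mohs.* It is not. Mohs carries an event only if the lesion recurs again and this is found at the visit; otherwise the lesion counts as a Mohs success. A shift of 2 × 0.34 = 0.68 points per lesion therefore requires a second recurrence.
- *That the bias can only favour eBx.* Exclusion 2, read study-wide, can remove Mohs failures that were later irradiated. Each lowers the Mohs rate by about 0.34 points and so works against eBx.

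**Conclusion.** The gap is plain in the text: there is no index-treatment rule, the prior-treatment exclusion runs in one direction, and the listed date can follow the later treatment. It should be closed. How often it bites is unknown, and so is the net direction, since losses can occur on both sides. The best-supported risk is an understated eBx recurrence rate, with irradiated skin in the Mohs toxicity and cosmesis ratings as a further consequence.

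The firm figures are 0.34 points per uncounted failure and about 4.4 expected recurrences per group. The probabilities in the sensitivity table illustrate assumed shares. They are not estimates for this study.

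**What to change.** - **7.6 and 8.1, group.** Assign each lesion to the first definitive treatment it received and keep it there whatever followed.
- **8.1, date.** Replace the listed date with the date on which that first course ended. Use it for the window, for calendar-year matching and for follow-up.
- **7.6.2, exclusion 2.** Restate it symmetrically as *any definitive treatment of this lesion before the index treatment*. This removes lesions first treated by some other method. An eBx course before the window also keeps a lesion out of Mohs. Treatment after the index course never excludes a lesion. A bare study-wide exclusion for radiation before Mohs would be wrong, because it would delete the eBx failures that need to be kept.
- **7.4 and 12.1, endpoint.** Count as an event any charted recurrence, or salvage treatment for recurrence, since the index course, in addition to status at the visit. Tick recurrence in the retrospective column as well, and record later treatments with their dates.

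**Cost.** A few lines of text and one or two extra chart items. A few Mohs candidates are lost, and the observed recurrence rates may rise slightly. No patient's care changes, since all lesions have already been treated.

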#### 2 PROTOCOL SYNOPSIS

STUDY NAME	CTPR-0014 Rev F March 7, 2017: A Multi-Center Retrospective- prospective Matched Pairs Cohort Study to Assess Clinical Outcomes of Lesions Treated with eBx Compared to Lesions Treated with Mohs Surgery
CO-PRINCIPAL INVESTIGATORS	[name] and [name]
SITES	Up to 5 sites will participate
STUDY DESIGN	This is a retrospective-prospective study design. Patients who completed treatment approximately 3 years (range of 2-4 years) at time of initial IRB approval of this study will be identified and any existing data in the patient's record will be collected in addition to conducting office visits for long-term follow-up. The study will include 2 parts:
	1. Retrospective chart review: Collect data from patient records who completed treatment a minimum of 2 years prior to study onset and determine the feasibility of doing a matched pair cohort study comparison of eBx versus Mohs surgery. The history, demographic and treatment data will be retrospectively collected from up to 320 subjects previously treated with eBx for the treatment of NMSC and up to 320 subjects previously treated with Mohs surgery for the treatment of NMSC.
	2. Prospective Follow-up: Patients will return for long-term follow-up visits for the investigators to assess the lesion site, document absence of recurrence/ absence of recurrence, toxicities, and collect patient reported outcomes.
SAMPLE SIZE	Up to 640 patients who will return for follow-up approximately 2 to 5 years post treatment so that at least 586 lesions have long term follow-up data collected. Follow-up may range from approximately 2 to 5 years post treatment. Up to 2 visits may be completed by each subject, one in 2016, and one in 2017-2018.
STUDY OBJECTIVES	
 
To evaluate local recurrence of eBx and Mohs treated lesions.
 
To evaluate toxicities related to eBx and Mohs treatments.
 
To evaluate cosmetic outcomes for lesions treated with eBx and Mohs.
 
To assess the ability to deliver therapy with eBx and Mohs treatment modalities.
 

PRIMARY ENDPOINT	Absence of local recurrence at approximately 3 to 5 year follow-up (range is approximately two to five years) at treatment site(s).

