SECONDARY ENDPOINTS	
 
Comparison of long-term toxicities related to eBx vs. Mohs treatment;
 
Comparison of long-term cosmetic outcomes for lesions treated for NMSC with eBx vs. Mohs;
 
Comparison of Chronic toxicities;
 
Comparison of Patient Reported Outcomes (PRO) using a patient survey.
 
	
ESTIMATED STUDY PERIODFollow-up Visits #1: August 29, 2016 – August 31, 2017 Data Collection & Data Entry: August 29, 2016 – September 31, 20		
	Prospective Follow-up Visit #2: August 31, 2017- January 31, 2018 Data Entry: August 1, 2017 – February 28, 2018	
SPONSOR & FUNDING PARTY	Xoft – a subsidiary of iCAD, Inc. San Jose, CA	
STATISTICAL ANALYSESXoft – a subsidiary of iCAD, Inc. San Jose, CA		
STUDY MANAGEMENT	Eminence Clinical Research, Inc. Colorado Springs, CO	
ELECTRONIC DATA CAPTURE	Eminence Clinical Research, Inc. Colorado Springs, CO	
MEDICAL WRITING ASSISTANCE	Eminence Clinical Research, Inc. Colorado Springs, CO	

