#### 7.4 Primary Endpoint

i. Freedom from local recurrence at the prospective follow-up visit in this study.

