#### 8.1.1 Step by Step Instructions

1. The eBx patients will be determined first. They are called consecutively based on the length of follow-up required by this protocol.

2. As patients are called back for consenting and follow-up visits begin, the patients treated with Mohs are called consecutively and asked to come back who match those treated with eBx.

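### Matching on calendar year of treatment does not by itself secure equal follow-up, and the primary comparison makes no allowance for time observed

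*Combined protocol and SAP*

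**What the plan says.** The first matching factor in Sections 8.1 and 8.2 is "Calendar year of treatment for equivalent follow-up". Last treatment date is among the record variables in Section 8.1, but it is not itself a matching factor.

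Section 8.1.1 sets the call order: "The eBx patients will be determined first. They are called consecutively based on the length of follow-up required by this protocol". Once eBx call-backs and visits are under way, "the patients treated with Mohs are called consecutively and asked to come back who match those treated with eBx".

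The Synopsis gives the first-visit window as "August 29, 2016 – August 31, 2017" and the second as "Prospective Follow-up Visit #2: August 31, 2017- January 31, 2018". Elsewhere the Synopsis says: "Up to 2 visits may be completed by each subject, one in 2016, and one in 2017-2018". The second visit is therefore optional, and the two accounts of when the first visit takes place do not agree. The Synopsis also allows follow-up of about 2 to 5 years.

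Section 7.4 defines the primary endpoint as "Freedom from local recurrence at the prospective follow-up visit in this study", without saying which visit. Section 12.2 summarises it by group with chi-square tests. The sample size rests on 1.5% recurrence at 3 years with Mohs, a 2.5% non-inferiority margin and 293 lesions per group.

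No section matches on visit date, limits the within-pair difference in follow-up, sets a common assessment time, or adjusts or censors for time observed.

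**The concern.** Follow-up runs from last treatment to assessment. The plan ties the first of these dates to a calendar year and leaves the second free. Recurrence accumulates with time, so a yes/no status read at unequal times mixes a treatment difference with a difference in observation time.

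Direction matters in a non-inferiority comparison. If eBx lesions are seen sooner after treatment than Mohs lesions, some eBx recurrences have not yet appeared, and the observed difference moves towards a finding of non-inferiority. With a 1.5% control rate and a 2.5-point margin, a few recurrences can decide the result. Long-term toxicity and cosmesis would also be rated at unequal times.

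**Working it through.** **1. The plan's sample size.** With p = 0.015 in both groups, margin d = 0.025, 80% power and one-sided 0.05:

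n = (1.645 + 0.842)² × 2 × 0.015 × 0.985 / 0.025² = 292.4, rounded up to 293.

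This reproduces Section 12.2. That section also says that all tests are two-sided at 0.05, which for non-inferiority corresponds to one-sided 0.025 (n = 372). Both levels are shown below.

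**2. How far follow-up can differ within one pair.**

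- Treatment dates in the same calendar year: up to 364 days.
- First visits, 29 Aug 2016 to 31 Aug 2017: 367 days. If the first visit must fall in 2016, 29 Aug to 31 Dec 2016: 124 days.
- Start of first visits to end of second visits, 31 Jan 2018: 520 days.

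The largest single-pair differences are 364 + 367 = 731 days (about 24 months) on first visits, 364 + 124 = 488 days (about 16 months) if first visits are confined to 2016, and 364 + 520 = 884 days (about 29 months) if only one member has a second visit. These are extremes for one pair, not average differences between groups.

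**3. How much time at risk can matter.** Assume a constant hazard at the plan's own Mohs rate: h = −ln(0.985)/3 = 0.00504 per year, with P(t) = 1 − exp(−ht). Then P(2) = 1.00% and P(5) = 2.49%. Across the permitted range the gap is 1.48 points, or 59% of the margin. This is a scale for the problem, not an estimate of bias.

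**4. Effect of an average eBx lag.** The lag is not in the documents; 1 to 3 months is an assumed range. Mohs is seen at 3 years (1.5%). eBx is truly on the margin: 4.0% at 3 years, so h = −ln(0.96)/3 = 0.01361 per year. The chance of wrongly passing is the exact binomial probability, with 293 per group, that difference + z × SE (Wald, unpooled) is below 2.5 points. Section 12.2 does not specify this bound, so it too is an assumption.

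| Mean lag | eBx recurrence at visit | Difference from Mohs | Wrongly passing, z = 1.645 | Wrongly passing, z = 1.96 |
|---|---|---|---|---|
| 0 | 4.00% | 2.50 points | 6.9% | 3.5% |
| 1 month | 3.89% | 2.39 points | 8.0% | 4.2% |
| 2 months | 3.78% | 2.28 points | 9.3% | 4.9% |
| 3 months | 3.67% | 2.17 points | 10.7% | 5.8% |

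The zero-lag values exceed 5% and 2.5% because the Wald bound is liberal at these rates, so the rise is what matters. A normal approximation at one-sided 0.05 gives 5.0%, 5.9% and 8.2% for lags of 0, 1 and 3 months.

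**5. Same lag, equal true hazards.** With h = 0.00504 in both groups, eBx appears better by 0.04 points (1 month) to 0.12 points (3 months), or about 0.1 to 0.4 recurrences in 293.

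**The case against.** The strongest reply is that nothing in the plan forces shorter eBx follow-up. Section 8.1.1 has Mohs calls start as the eBx call-backs and visits begin, so the two streams overlap. It also ties eBx calling to the length of follow-up required. Treatment-date differences within a year, and uptake of the second visit, could favour either group. Section 12.2 compares group summaries, so only the mean difference in follow-up biases the result, and opposite differences between pairs largely cancel. All of this stands.

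A reader might infer two stronger things. The first is that eBx lesions will be seen 6 or 12 months earlier on average. Under the same model that would put the chance of wrongly passing at 16% or 34% (one-sided 0.05). The documents do not support this. A 12-month mean lag at first visits needs essentially every eBx visit at the start of the 367-day window and every Mohs visit at its end. With visits spread evenly, a 6-month lag needs all eBx visits in the first half and all Mohs visits in the second. Rolling calls fit neither; weeks to a few months is more plausible. The second is that the 24- or 29-month gap measures the bias. It is a single-pair extreme.

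The reply does not remove the core point. No provision makes follow-up equivalent, and the analysis would not correct for it if it were not.

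**Conclusion.** The point holds as a gap in the plan: calendar-year matching does not deliver the equivalence it is credited with, the endpoint visit is undefined, and the analysis ignores time at risk. It does not hold as a demonstrated bias in favour of eBx. The only source with a likely direction is the call order, and its probable size is modest: 6.9% rising to 8.0–10.7% at one-sided 0.05, or 3.5% rising to 4.2–5.8% at one-sided 0.025, for a mean lag of 1 to 3 months. If eBx and Mohs truly recur at the same rate, the effect is negligible.

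These figures rest on the assumed lag, constant hazards, eBx exactly at the margin, Mohs seen at 3 years, a Wald bound and independent lesions. The documents give neither the actual lag nor second-visit attendance. This is a cheap improvement that removes an avoidable source of bias.

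**What to change.** **Section 7.4.** State how the two visits define the endpoint, for example local recurrence at any assessment up to the last visit. Reconcile the two Synopsis statements on when the first visit takes place.

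**Section 12.2.** Make the primary comparison the difference in recurrence proportion at a common time, such as 3 years, with its confidence bound set against the 2.5-point margin. Take it from a time-to-event estimate that starts at last treatment date and censors at last assessment. Treat recurrence as interval-censored, since it is known only to the visit or record at which it was found. Report follow-up time by group.

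**Sections 8.1, 8.1.1 and 8.2.** Where several Mohs lesions match, prefer the one with the closest last treatment date, and call both members of a pair at about the same time. Do not impose a hard window on follow-up time, because some pairs could not meet it. Suppose an eBx lesion treated on 15 Dec 2013 is seen on 1 Sep 2016. A Mohs match treated on 15 Jan 2013 would need a visit around October 2015, before study visits began. Losing such pairs would put the 293 at risk.

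**Cost.** There is slightly more analysis work, and the interval may be slightly wider. Visit date and date of recurrence detection must be recorded on the follow-up form. Last treatment date is already listed, but the case report form is a separate document, so the protocol does not show whether the other two dates are captured. If visits are already complete, the analysis and reporting changes can still be made.
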